5.2 Withdrawal from the Study, Discontinuation of Investigational Product, or Study Termination

5.2.1 Withdrawal from the Study or Discontinuation of the Investigational Product

Subjects are free to withdraw from the study at any time upon request. Subject participation in the study may be stopped at any time at the discretion of the Investigator or at the request of the Sponsor.

The Sponsor will be notified in advance whenever possible if subjects are stopped at the discretion of the Investigator. When a subject withdraws from the study or is stopped, the reason(s) are to be recorded by the Investigator on the relevant page of the electronic case report form (eCRF). Whenever possible, any subject who withdraws or is stopped from the study prematurely will undergo all ET assessments. Any subject who fails to return for final assessments will be contacted by the clinical site in an attempt to have them comply with the protocol. The status of subjects who fail to complete final assessments will be documented in the eCRF.

The reasons for stopping subject participation by the Investigator or Sponsor include, but are not limited to the following:

- The subject meets individual halting criteria (Section 8.6.2).
- Subject noncompliance based on any of the following criteria after IP administration and before completion of all follow-up visits through Day 120 (±5):
 - Positive urine drug screen
 - Has major surgery
 - Received another IP
 - Uses prohibited medication
 - Receives blood products or donates blood or plasma
- An AE or new clinical finding(s) for which continued participation, in the opinion of the Investigator, might compromise the safety of the subject, interfere with the subject's successful completion of this study, or interfere with the evaluation of responses.
- The subject is lost to follow-up.
- Subjects becoming pregnant prior to or following IP administration prior to the final follow-up visit on Day 120 (±5). Subject becoming pregnant after IP administration will not be included in data analysis but will be followed for safety.

If the subject consents, every attempt will be made to follow all AEs through resolution including those subjects that elect to withdraw. The procedures that collect safety data for the

purposes of research must be inclusive in the original ICF or the Investigator may seek subsequent informed consent using an IRB-approved consent form with the revised procedures.

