10.4.1 Populations for Analysis

The analysis populations are as follows:

- The safety population will include all subjects who receive the full dose of the IP.
- The PK population will include subjects who receive the full dose of AV-1 and have at minimum all samples from predose through 1.5 hours from the start of infusion to have sufficient concentration data to support accurate estimation of at least 1 PK parameter.

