10.4.2 Statistical Analyses

Details of all statistical analyses will be described in a separate statistical analysis plan. All data collected will be presented in data listings. Data from subjects excluded from an analysis population will be presented in the data listings, but not included in the calculation of summary statistics.

For categorical variables, frequencies and percentages will be presented. Continuous variables will be summarized using descriptive statistics (number of subjects, mean, standard deviation [SD], minimum, median, and maximum).

All subjects receiving placebo across cohorts will be pooled into 1 treatment group for summary purposes.

Baseline demographic and background variables will be summarized overall for all subjects. The number of subjects who enroll in the study and the number and percentage of subjects who complete the study will be presented. Frequency and percentage of subjects who withdraw or discontinue from the study, and the reason for withdrawal or discontinuation, will also be summarized.

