4.2. Analysis Populations

The Safety population will include all subjects who receive any amount of the IP. The safety population will also be used for anti-AV-1 antibody assessment.

The PK population will include subjects who receive the full dose of AV-1 and have at minimum all samples from predose through 1.5 hours from the start of infusion to have sufficient concentration data to support accurate estimation of at least 1 PK parameter.

5. Subject Disposition, Protocol Deviations, and Follow-up

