8.4. Pharmacokinetic Statistical Analysis

Dose-proportionality for AV-1 will be evaluated for C_{max} , AUC_{0-tlast}, and AUC_{0- ∞}. A power model will be fitted to describe the relationship between Y (C_{max} , AUC_{0-tlast} and AUC_{0- ∞}) and X (dose) using the least-squares linear regression model [ln(Y) = ln(β_0) + β_1 ln(X)].

From each model, the intercept of regression line $[\ln(\beta_0)]$ and the slope of the regression line β_1 will be presented along with the 90% confidence interval (CI) of the slope. Dose-proportionality will be concluded if the 90% CI of the slope β_1 lies entirely within $[1+\ln(0.8)/\ln(r), 1+\ln(1.25)/\ln(r)]$, where r is a ratio that describes the dose range and is defined as the ratio of highest dose/lowest dose. If dose proportionality is not observed, then the lowest dose followed by the highest dose in succession will be removed, and the model will be fit again after the removal of a dose until dose proportionality is achieved or less than 3 dose groups remain.

The statistical analyses will be based on the PK population.

9. Anti-AV-1 Antibody Analysis

Blood samples for immunogenicity analysis will be collected at Check-in (Day -1) and on Days 29 (±2), 85 (±5), and 120 (±5) (or ET). A validated ECL ELISA method will be used for detection and confirmation of preexisting and treatment-emergent anti-AV-1 antibodies in serum samples based on the MesoScale Discovery platform that utilizes labeled AV-1 for detection of anti-AV-1 antibodies and treatment emergent antibodies.

Frequency and percentage of subjects who show detectable anti-AV-1 antibody signal in serum, including treatment-emergent anti-AV- antibodies, will be summarized for the safety population. Pharmacokinetic parameters may be displayed based on anti-AV-1 antibody status as applicable.

Anti-AV-1 antibody data will be presented in a data listing for the safety population.

10. Safety Analysis

All safety summaries and analyses will be conducted for the safety population.

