10.1. Adverse Events

An AE is defined by ICH E6(R2) as any untoward medical occurrence in a patient or clinical investigation subject administered a pharmaceutical product regardless of its causal relationship to the study treatment.

An AE can therefore be any unfavorable and unintended sign (including an abnormal laboratory finding), symptom, or disease temporally associated with the use of medicinal (investigational) product. The occurrence of an AE may come to the attention of study personnel during study visits and interviews of a study recipient presenting for medical care, or upon review by a study monitor. All AEs, including solicited local (infusion site) and systemic (subjective and quantitative) reactions, will be captured on the appropriate data collection form and in the eCRF.

A treatment-emergent AE (TEAE) is defined as any event that does not present before exposure to study drug or any event already present that worsens in intensity or frequency after exposure.

Only TEAEs will be included in summary tables.

Adverse events will be coded by preferred term (PT) and system organ class (SOC) using MedDRA (version to be delineated in the CSR).

A subject may have more than 1 AE for an SOC or PT. A subject with 2 or more AEs within the same level of summarization will be counted only once in that summarization level. In addition to the summarization of subjects with AE at each level, the frequencies of AE occurrences will also be summarized at each level. Percentages will be based upon the number of subjects in the safety population for each treatment group.

All AEs will be presented in a data listing.

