10.1.1. Incidence of Adverse Events

An overview of AEs will be presented by treatment and total, including number and percentage of subjects with any:

- Treatment-emergent AE
- Treatment-related TEAE
- Moderate TEAE

- Treatment-related moderate TEAE
- Severe TEAE
- Treatment-related severe TEAE
- Serious TEAE
- Treatment-related Serious TEAE
- Treatment-emergent AE leading to early discontinuation
- Death

All TEAEs will be presented in a summary table by treatment and total for each SOC and PT. Percentages will be calculated out of the number of subjects in the safety population.

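### Protocol 5.2.1 bars a dosed subject who becomes pregnant from data analysis. This conflicts with the same section's closing sentence and with both safety populations, and the SAP does not declare the departure.

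*Protocol*

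**What the plan says.** Protocol 5.2.1 lists reasons for stopping a subject's participation. One is pregnancy before the final follow-up visit on Day 120 (±5), and for this case the section adds: "Subject becoming pregnant after IP administration will not be included in data analysis but will be followed for safety". The same section ends by having the Investigator tell subjects that data collected up to a withdrawal are kept and analysed. That sentence makes no exception for pregnancy.

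The population definitions do not mention pregnancy. Protocol 10.4.1 says: "The safety population will include all subjects who receive the full dose of the IP". SAP 4.2 says: "The Safety population will include all subjects who receive any amount of the IP", and adds: "The safety population will also be used for anti-AV-1 antibody assessment". The PK population, worded alike in both documents, has no pregnancy rule either.

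The SAP rests the safety tables on its own definition. Section 10 says: "All safety summaries and analyses will be conducted for the safety population". For adverse events, 10.1 says: "Percentages will be based upon the number of subjects in the safety population for each treatment group". Section 11 declares one departure from the protocol, full dose to any amount, and is silent on the pregnancy sentence.

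**The concern.** Safety is the primary objective, and the exclusion depends on something that happens after dosing. Read literally, it also reaches data that the pregnancy could not have influenced. Subjects stay in the clinic from Day -1 to discharge on Day 5, so for a pregnancy that begins after discharge, the infusion-day observations and the rest of the inpatient safety data all come before it.

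Two analysts working in good faith could produce different tables. One follows the SAP and keeps her. The other treats the protocol sentence as a standing rule that the SAP did not revoke, and drops her. Groups are small, so one subject visibly moves a percentage. The antibody summaries share the safety population, so a secondary objective is exposed as well. If the question is settled only after such a pregnancy occurs, it may be settled with her data already known.

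**Working it through.** **Step 1: compare the texts for a dosed subject who becomes pregnant before Day 120.**

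| Source | Is she in the safety summaries? |
|---|---|
| Protocol 5.2.1, pregnancy sentence | No, if it is read to cover safety data |
| Protocol 5.2.1, closing sentence | Her data so far are analysed, if she counts as withdrawn |
| Protocol 10.4.1 | Yes, if fully dosed |
| SAP 4.2 and Section 10 | Yes |
| SAP Section 11 | Silent |

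A version difference does not explain the gap. The SAP cites Protocol Amendment 2, and the logged changes for Amendments 3 and 4 concern key personnel and exclusion criterion 23, not 5.2.1. The SAP's one analysis statement on pregnancy (10.2) says that pregnancy test results are not summarised. It does not address who is included.

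**Step 2: group sizes.** Protocol 10.2 gives 6 AV-1 and 2 placebo subjects per cohort in 5 cohorts. Then 5 × (6 + 2) = 40, which reproduces the stated total, and pooled placebo is 5 × 2 = 10. The AE tables show each dose level, pooled placebo and a total column (SAP Section 4 and 10.1.1: "An overview of AEs will be presented by treatment and total").

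**Step 3: effect per excluded subject.** The documents give no pregnancy rate, so no probability is attached. Assume one subject with the event in the column shown, and no replacement. Excluding her turns 1/n into 0/(n − 1) if the event was hers, or 1/(n − 1) if it was not.

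| Column | Kept | Excluded, event hers | Excluded, event another's |
|---|---|---|---|
| Dose group | 1/6 = 16.7% | 0/5 = 0% | 1/5 = 20.0% |
| Pooled placebo | 1/10 = 10.0% | 0/9 = 0% | 1/9 = 11.1% |
| Total | 1/40 = 2.5% | 0/39 = 0% | 1/39 = 2.6% |

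**Step 4: with a replacement.** Protocol 10.2 allows up to 8 replacements, and 5.2.2 makes replacement discretionary for a subject who withdraws. Assume that this rule is used for her and that the replacement has no event. The dose group is then 1/7 = 14.3% with her kept, and 0/6 = 0% or 1/6 = 16.7% with her excluded. Pooled placebo is 1/11 = 9.1% against 0/10 = 0% or 1/10 = 10.0%. The total is 1/41 = 2.4% against 0/40 = 0% or 1/40 = 2.5%. A replacement can restore the denominator but not her events.

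**The case against.** The strongest reply is that the SAP already settles the matter. Protocol 10.4 and 10.4.2 leave the details of all analyses to the SAP. The SAP includes everyone who received any IP, and a programmer working from it alone keeps her. This stands, and it is the main reason why the point is minor. It does not remove the inconsistency: Section 11 exists to declare departures from the protocol, and this one is missing from it.

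A second reply is that the sentence may be meant more narrowly, since it provides for safety follow-up and the section's closing sentence keeps data already collected. The scope is indeed open. But the sentence sets follow-up against inclusion in analysis, and no PK population or other rule carries out a narrower meaning. The closing sentence speaks of a subject who withdraws, so its use for a subject stopped for pregnancy is arguable. Even so, it leaves 5.2.1 inconsistent on its face.

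A reader might also infer three stronger conclusions that the documents do not support.
- *The planned safety tables will omit her.* Under the SAP as written, they will not.
- *She would be moved to listings only, as a stated rule.* Protocol 10.4.2 says: "Data from subjects excluded from an analysis population will be presented in the data listings, but not included in the calculation of summary statistics". No population definition excludes her, so this follows only if 5.2.1 is first read as amending one.
- *Her events would escape safety oversight.* The sentence itself keeps her under follow-up, and nothing in it takes her events away from the safety review or safety monitoring committee.

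Finally, entry requires negative serum pregnancy tests at Screening and Day -1, together with contraception, abstinence, or postmenopausal or sterile status. The trigger is therefore unlikely.

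**Conclusion.** The inconsistency is real and the point is minor. Protocol 5.2.1 contains an exclusion of unstated scope that conflicts with its own closing sentence and with both safety populations, and the SAP overrides it only by implication.

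The percentages above are conditional. They need a pregnancy after dosing, the protocol sentence to be applied over the SAP, and exactly one subject with the event in the column. Under those assumptions a dose-group figure of 16.7% becomes 0% or 20.0%, so the direction depends on whose event it was. The total column moves from 2.5% to 0% or 2.6%.

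No formal safety hypothesis is at risk. Protocol 10.1 says in general terms that none is tested, although 10.4.3 and SAP 8.4 do set up a dose-proportionality assessment with a null slope of 1 and a confidence-interval rule. The sentence could reach that analysis too if it were applied to PK data. Her data remain in the listings in any case.

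**What to change.** In Protocol 5.2.1, delete the clause that bars her from analysis, so that the sentence only provides for safety follow-up. The rule on stopping participation is untouched.

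In SAP Section 11, state that, contrary to that protocol sentence, every subject who received any amount of IP stays in the safety and antibody summaries regardless of later pregnancy, and that PK inclusion follows the existing PK population definition.

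Do not confine the exclusion to PK samples taken after pregnancy onset instead. That would be a new rule without support in the documents. By cutting the profile short it could move the last quantifiable point earlier and lower AUC0-tlast, which enters the dose-proportionality model.

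The cost is one shortened protocol sentence and one added SAP sentence, with no extra visits, samples or subjects.

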5.2.2 Subject Replacement

Any subject who withdraws before completing the study but after receiving IP may be replaced at the discretion of the Investigator and in consultation with the Sponsor. Any replacement subject will be assigned to receive the same treatment as the subject he or she is replacing.

5.2.3 Study Termination

Although the Sponsor has every intention of completing the study, they reserve the right to discontinue it at any time for clinical or administrative reasons.

If the study is prematurely terminated by the Sponsor, any regulatory authority, or the Investigator for any reason, the Investigator will promptly inform the study subjects and assure appropriate therapy or follow-up for the subjects, as necessary. The Investigator will provide a detailed written explanation of the termination to the IRB.

The end of the study is defined as the date on which the last subject completes the last visit (including the ET visit and any additional long-term follow-up). Any additional long-term follow-up that is required for monitoring of the resolution of an AE or finding may be appended to the clinical study report.

6 STUDY PROCEDURES

Before performing any study procedures, all potential subjects will sign an ICF as outlined in Section 9.2.

A complete schedule for all study procedures is detailed in the schedule of events (Section 17.1).

The IP will be administered in the clinical unit under direct observation of clinic personnel and will be recorded in the eCRF. Clinic personnel will confirm that the subject has received the entire dose of the IP. Complete information regarding any partial or interrupted infusions will be documented. The date and time (start and stop) of IP dosing will be recorded on the appropriate page in the eCRF.

A study physician will be present at the time of IP administration and the subject will be under observation during the 60-minute infusion. Vital signs will be monitored, and an ECG will be recorded prior to, during, and after the infusion as outlined in the schedule of events (Section 17.1). The study site staff will observe the subjects closely for signs and symptoms of infusion-related reactions, including anaphylaxis and anaphylactoid type reactions. Should an adverse reaction of this type occur, the subject will be treated using the standard protocol at the clinical site. Infusion-related AEs and suspected hypersensitivity reactions will be documented, including the clinical presentation and severity (based on the grading scales in Section 17.2) of the event.

For the specified time points, PK sample collection will take precedence over all other study sampling procedures and will therefore occur at the nominal time as described in Section 7.2.2. Multiple non-PK study procedures scheduled at the same time point should be performed as close as possible to the nominal time point (within 60 minutes predose and within 30 minutes for postdose time points). When procedures overlap or occur at the same time point, all blood draws should follow ECGs or vital signs, and PK sampling should be timed to occur last and as close to the scheduled time window as possible. The total amount of blood collected from each subject over the duration of the study, including any extra assessments that may be required, will not exceed 500 mL. Refer to the laboratory manual for specific details on blood volumes used for laboratory testing.

7 DESCRIPTION OF CLINICAL AND LABORATORY EVALUATIONS

The timing and frequency of all safety assessments are listed in the schedule of events (Section 17.1).

7.1 Clinical Evaluations

Safety endpoints will include monitoring and recording of AEs and SAEs, clinical laboratory test results (hematology, chemistry, and urinalysis), vital sign measurements, 12-lead ECG results, and physical examination findings.

For all safety assessments, the Investigator will determine whether results are clinically significant, which is defined as any variation in a result that has medical relevance and may result in an alteration in medical care (eg, active observation, diagnostic measures, or therapeutic measures). If clinical significance is noted, the result and reason for significance will be documented on the AE page in the subject's eCRF and the Investigator will monitor the subject until the result has reached the reference range or the result at Screening, or until the Investigator determines that follow-up is no longer medically necessary.

7.1.1 Vital Signs

Vital sign measurements will include systolic and diastolic blood pressure, oral body temperature, heart rate, and respiratory rate. The subject will have rested comfortably in a seated or supine position for at least 5 minutes before all measurements are taken. For time points when ECGs and vital signs occur at the same time point, it is acceptable to perform the vital sign measurements approximately 2 minutes after the ECG as long as the subject remains resting in the supine position. Additional vital signs may be measured for safety of the subjects at the discretion of the Investigator. All measurements will be recorded in the subject's eCRF.

7.1.2 Twelve-lead ECG

Twelve-lead ECG recordings will be obtained after the subject has rested comfortably in a supine position, for at least 10 minutes. The Investigator should review and sign the ECG for any immediate issues. Electrocardiogram assessments will include comments on whether the tracings are normal or abnormal, rhythm, presence of arrhythmia or conduction defects, morphology, any evidence of myocardial infarction, or ST-segment, T-wave, and U-wave abnormalities. In addition, measurements of the following intervals will be measured and reported: RR interval, PR interval, QRS width, and QTcF.

7.1.3 Medical History

Medical history will be obtained by direct interview and include a history of significant medical disorders of the head, eyes, ears, nose, throat, cardiovascular system, lungs, gastrointestinal tract,

liver, kidney, urologic, nervous system, blood, lymph glands, endocrine system, musculoskeletal system, skin, and genital/reproductive tract. A history of any allergies, cancer, immunodeficiency, psychiatric illness, substance abuse, and autoimmune disease will be solicited. The medical history will include current and past medical diagnoses, hospitalizations, and major surgical procedures.

At each visit, subjects will be asked about any changes in health, new or worsening symptoms, or medications taken since their last visit. Any new adverse health changes will be recorded as an AE.

7.1.4 Physical Examination

A full physical examination will be performed at Screening (skin, head, ears, eyes, nose, throat, neck, thyroid, lungs, heart, cardiovascular, abdomen, lymph nodes, and musculoskeletal system/extremities). Focused examination (lungs, cardiovascular, abdomen, and skin) will be performed at Check-in (Day –1) and on Days 5, 8, and 15. Targeted, symptom-directed physical examinations will be performed at all other follow-up visits.

